Participants found to be pregnant will be counseled on referral options and supported as needed with rapid referral for OB care at the UW Northgate Family Medicine Clinic, as well as follow up at SHE Clinic. Participants will be counseled on PrEP and MOUD safety and efficacy during pregnancy.

Management of viral hepatitis

Participants diagnosed with hepatitis B virus (HBV) and/or hepatitis C virus (HCV) will be counseled on strategies to prevent transmission and referred to SHE Clinic for further evaluation and management.

Management of acute opioid overdose or severe intoxication

In the event that participant presents to the research clinic and is found to be severely intoxicated or experiencing an acute opioid overdose, emergency medical personnel will be called for transport to a local emergency department. In the case of an opioid overdose, the individual will be given intranasal Narcan by research clinic staff.

Research Reimbursement and Incentives

Participants will receive up to a total of \$75 in reimbursement for participating in this study. They will be reimbursed \$25 for the baseline study visit, \$25 for the 3-month study visit, and \$25 for the 6-month study visit. Reimbursement will be provided in the form of a Visa gift card, that will be giving to the participant at each study visit. Participants who return to the venue-based clinic between study visits for clinical care will not be reimbursed for interim visits. Participants who return to the research clinic to receive results of laboratory tests will receive an additional \$15 incentive for follow-up. Persons who are not participants in this study but access the venue-based clinic for standard of care will not receive any reimbursement or financial incentive. Study team members will retain a log of each reimbursement provided, and participants will be asked to sign their initials on the log to confirm receipt of each \$15 Visa gift card.

Protection of Human Subjects

Involvement of Human Subjects

This is a prospective observational cohort study, which aims to enroll 50 women who inject drugs in a venue-based clinic. Study participants will be offered HIV PrEP and buprenorphine for treatment of opioid use disorder, as indicated by national guidelines. The main objective is to

assess the impact of venue-based care on uptake and sustained use of PrEP and buprenorphine for the prevention of HIV and treatment of opioid use disorder, respectively.

Research Material Obtained from Participants

Individuals who are eligible and enroll in venue-based care will complete a baseline, 3-month and 6-month study visit. Data to be collected at those visits include information on demographics, risk factors for HIV, PrEP eligibility, prior use of PrEP, history of substance use, prior use of medications for opioid use disorder (MOUD), current use of MOUD, and self-reported adherence to PrEP and/or MOUD, as indicated. Participants will also provide information on their experience accessing venue-based care, including acceptability and perceived stigma associated with accessing venue-based care. POC HIV testing, POC STI testing, and standard of care labs for PrEP will be obtained at baseline, 3-months and 6-months. Hair samples and DBS samples to test for tenofovir and buprenorphine will be obtained at 3-month and 6-month visits. A review of the participants medical and pharmacy records will be conducted.

Assessment data will be collected directly onto iPads used by research team members. We will utilize the Research Electronic Data Capture (REDCap) system through the University of Washington's Institute of Translational Health Services (ITHS) to log and store data.

Women who are started on buprenorphine therapy will also return for monthly refill visits, during which time no additional study data will be collected.

Risks to Human Subjects

There are limited physical risks to study subjects beyond what is incurred during standard primary care. Participants may experience mild bruising or pain at the site of point of care finger prick testing (e.g., POC HIV and syphilis testing, DBS sampling), or at the site of phlebotomy draws. Participants who choose to initiate on oral PrEP and/or buprenorphine will be at risk of experiencing established side effects, as outlined in each drugs' prescribing materials.

Participants may experience psychological distress associated with discussing confidential topics such as sexual and drug use practices. Research medical team staff will be trained in trauma-informed care and to address psychological distress with a calm, non-judgmental attitude. We will take steps to minimize any psychological discomfort by ensuring confidentiality as described below. We will only enroll patients who understand the study procedures and are willing to participate.

Participants may also experience loss of confidentiality related to study visits, which is likely the most serious risk of the study. We take this risk seriously, and we will take steps to protect participants' confidential data and anonymity. All subjects will be informed of risks and provide their consent prior to enrollment.

Adequacy of Protection Against Risks

Risks of psychological distress from the research assessments will be minimized by using research medical staff that are trained in how to provide trauma-informed care. Participants may choose to leave the study visit at any time. If consequences arise due to research procedures (e.g., distress, anxiety, suicidal thoughts), then the physician investigators will be available to assess subjects in real time and make appropriate interventions or referrals based on the clinical circumstances.

Loss of confidentiality is very unlikely given the structures that will be put in place to avoid inadvertent disclosure. These structures to assure confidentiality include the following: each subject will receive a unique identification number, and research data collection and data entry forms will be electronic and identified only with this number. Only the master enrollment list and electronic informed consent forms will have identifying information on them. These documents will be kept on secure University of Washington servers / in REDCap, accessible only to principal investigators, the research assistant and research coordinator. Tracking information will be kept similarly. Computer data will be password protected and accessible only to research staff needing the information for follow-up and monitoring purposes. Files stored on UW servers will be protected by electronic firewalls that restrict access to designated users.

Another possible threat to confidentiality could arise if a participant indicates an imminent danger to self or others or if a participant discloses abuse of vulnerable persons such as children, the elderly, or the disabled. Ethical and legal requirements may force us to disclose this type of information to relevant authorities. We will attempt to minimize this threat to confidentiality by clearly informing participants of the risks involved during the informed consent process.

Potential Benefits

Participants may benefit from access to research POC STI testing, which is not generally commercially available. Participants may similarly benefit from the reimbursement provided for attending study visits and returning for lab results.

Importance of Knowledge to be Gained

The study will inform us about the ability of venue-based care to improve and support uptake and sustained use of critical HIV prevention interventions, including PrEP and buprenorphine, for women who inject drugs, many of whom also engage in exchange sex. It will also inform us about the acceptability and feasibility of providing venue-based care for women who inject drugs. If the study demonstrates benefit of venue-based care, this would provide evidence that this type of intervention should be studied at scale.

Electronic Health information

This novel venue-based clinic will be integrated within the larger University of Washington (UW) healthcare system, and necessary referrals will be made to UW facilities, including a large UW medical campus located two miles north of Aurora Commons. Participants not already registered in UW system will receive a medical record number and clinical portion of study visits will be included in electronic medical records to improve overall continuity of care. Participants will consent to a review of their health information in the UW Epic EHR system and review of local pharmacy records.

Incarcerated Participants

As per NIH guidance, research participants who become incarcerated during the study will be temporarily withdrawn from the study until OHRP guidelines are met. When subjects are incarcerated their buprenorphine and PrEP treatment may not be continued, and they do not have access to cell phones, so they cannot continue participation for these reasons. When subjects become released from incarceration, we will resume study procedures. If research staff members are unable to contact a participant who has missed an appointment or cannot be reached to remind them of an upcoming research visit, research staff should check the local law enforcement databases to determine if the study participant is incarcerated.

Important Definitions

Adverse Event (AE)

Any unfavorable and unintended sign (including an abnormal laboratory finding), symptom or disease temporally associated with the use of a medical treatment or procedure, regardless of whether it is considered related to the medical treatment or procedure.

Serious Adverse Event (SAE)

Any adverse event that results in any of the following outcomes:

- Death
- Life-threatening
- Event requiring inpatient hospitalization or prolongation of existing hospitalization
- Persistent or significant disability/incapacity
- Results in birth defect

Unanticipated problems/events

They must meet all of the following criteria (per UW definition):

- 1) Unexpected-- The harm (or potential harm) is inconsistent with risk information previously reviewed and approved by the Institutional Review Board (IRB) in terms of nature, severity, or frequency as well as the characteristics of the study population
- 2) Related or probably related to participation in the research. Probably related: there is reasonable (more likely than not) that the incident, experience or outcome may have been caused by the procedures involved in the research, or that it is associated with the use of any drug, biologic, or medical device that is part of the research.
- 3) Suggests that the research placed (or did place) one or more subjects or other a greater risk of harm than was previously known or recognized. This includes physical, psychological, economic, educational advancement, or social harm.

Classifying adverse events

Adequate review, assessment, and monitoring of adverse events require that they be classified as to **severity**, **expectedness**, and potential **relatedness** to the study intervention. Study protocols will include a description of how adverse events will be classified in these terms and the appropriate course of action.

Severity

Classifications often include the following:

- **Mild:** Awareness of signs or symptoms, but easily tolerated and are of minor irritant type causing no loss of time from normal activities. Symptoms do not require therapy or a medical evaluation; signs and symptoms are transient.
- **Moderate:** Events introduce a low level of inconvenience or concern to the participant and may interfere with daily activities, but are usually improved by simple therapeutic measures; moderate experiences may cause some interference with functioning
- **Severe:** Events interrupt the participant's normal daily activities and generally require systemic drug therapy or other treatment; they are usually incapacitating

Severity is not synonymous with seriousness. A **severe** rash is not likely to be an **SAE**.

Likewise, a **severe** headache is not necessarily an **SAE**. However, **mild** chest pain may result in a day's hospitalization and thus is an **SAE**.

Expectedness

AEs must be assessed as to whether they were expected to occur or unexpected, meaning not anticipated based on current knowledge found in the protocol, investigator brochure, product insert, or label. Categories are:

- **Unexpected** - nature or severity of the event is not consistent with information about the condition under study or intervention in the protocol, consent form, product brochure, or investigator brochure.
- **Expected** - event is known to be associated with the intervention or condition under study.

Relatedness

The site investigator assesses the potential event relationship to the study intervention and/or participation. A comprehensive scale in common use to categorize an event is:

- **Definitely Related:** The adverse event is clearly related to the investigational agent/procedure – i.e. an event that follows a reasonable temporal sequence from administration of the study intervention, follows a known or expected response pattern to the suspected intervention, that is confirmed by improvement on stopping and reappearance of the event on repeated exposure and that could not be reasonably explained by the known characteristics of the subject's clinical state.
- **Possibly Related:** An adverse event that follows a reasonable temporal sequence from administration of the study intervention follows a known or expected response pattern to the suspected intervention, but that could readily have been produced by a number of other factors.
- **Not Related:** The adverse event is clearly not related to the investigational agent/procedure. - i.e. another cause of the event is most plausible; and/or a clinically plausible temporal sequence is inconsistent with the onset of the event and the study intervention and/or a causal relationship is considered biologically implausible.

Data Safety Monitoring Plan

The principal investigators (MPIs) will be responsible for ensuring participant safety on a day-to-day basis. The MPIs ([name] and [name]) along with the Data Safety Monitoring Board (DSMB) will oversee the safety of participants and the validity and integrity of the data. Drs. [name] and [name] will be responsible for selecting the DSMB members and ensuring they have no conflicts of interest with the current study or principal investigators.

DSMB Responsibilities

The DSMB will be responsible for reviewing and evaluating the study protocols, plans for participant safety, and data monitoring plan prior to study enrollment. The DSMB will also evaluate the study progress, including participant recruitment, enrollment, and retention, data collection, and general operations of the venue-based clinic. The DSMB will evaluate for treatment harm or benefit, including individual AEs and SAEs, and make decisions regarding the continuation, modification or termination of the study based on these data. The DSMB will also review external information, if relevant to the study, that might affect the ethics of study continuation (e.g., new therapeutic advances that impact standard of care).

Cadence of DSMB meetings

The DSMB will meet remotely with study MPIs:

1. Prior to enrollment
2. Once the study has reached 50% enrollment (n=25)
3. At least every 6 months thereafter while the study is active.

Following each meeting, the DSMB will make recommendations on continuation, modification, or termination of the study. Aside from these regular meetings, an unanticipated AE may prompt an ad hoc report to be distributed and may result in an ad hoc teleconference for the entire DSMB. Upon study completion no additional meetings will be required of the DSMB.

DSM Reporting

Following each meeting the DSMB will produce a report that will be sent to the UW IRB within 10 days and to NIDA within 30 days of the DSMB meeting. The report will include a meeting summary, DSMB recommendations regarding the continuation, modification, or termination of the research project, and any other specific recommendations put forth by the DSMB.

Analysis Plan

1. Evaluate uptake of PrEP:
 - a. Defined as the proportion of participants who accept a prescription for PrEP from the study team at any point (i.e., baseline, Month 3, and/or Month 6 visit) during study participation. The denominator will be all participants (N=50) enrolled in the study.
 - b. Participants who accept prescriptions for PrEP at multiple points throughout the study will only be counted once when calculating uptake.
 - c. Final analysis will present uptake as a percentage (proportion).
2. Evaluate uptake of MOUD
 - a. Defined as the proportion of participants who accept a prescription for MOUD from the study team at any point (i.e., baseline, Month 3, and/or Month 6 visit) during study participation. The denominator will be all participants (N=50) enrolled in the study.
 - b. Participants who accept prescriptions for MOUD at multiple points throughout the study will only be counted once when calculating uptake.
 - c. Final analysis will present uptake as a percentage (proportion).
3. Evaluate sustained use of PrEP
 - a. PrEP: Dried blood spot (DBS) samples were obtained at each visit to assess PrEP adherence via tenofovir-diphosphate (TFV-DP) concentrations. Sustained use was defined as >4 doses/week, resulting in a DBS TFV-DP concentration of >700 fmol/sample at 3 and/or 6 months post-enrollment among those prescribed PrEP at a preceding study visit.
 - b. Final analysis will present sustained use for both PrEP as a percentage (proportion).
4. Evaluate sustained use of MOUD
 - a. MOUD: DBS samples were obtained at each visit to assess MOUD adherence via buprenorphine and norbuprenorphine concentrations, both measured in ng/mL. Sustained use was defined as any buprenorphine and/or norbuprenorphine detected, resulting in a DBS >0 ng/mL concentration of buprenorphine and/or norbuprenorphine at 3 and/or 6 months post-enrollment among those prescribed MOUD at a preceding study visit.
 - b. Final analysis will present sustained use for MOUD as a percentage (proportion).
5. Evaluate STI treatment completion rate and time to completion after POC STI testing
 - a. Treatment completion will be defined as documented treatment following a reactive POC STI test (chlamydia, gonorrhea, syphilis, and/or trichomonas). Treatment will either be indicated in the Visit Clinical Summary from the study visit or noted during medical record chart review by a study provider. If treatment

was not provided on the same day as the visit, the date of treatment will be documented in the study database.

- b. Final analysis will present the treatment completion rate as the proportion of STIs where treatment was documented, by all STIs and by type.
 - c. Final analysis will present the time to treatment completion as the proportion of STIs treated same-day. Of the STIs not treated same-day, time to treatment will be presented as median number of days with an interquartile range.
6. Assess acceptability of pilot community-based care model
- a. Participants completed an acceptability survey following each study visit. Acceptability will be presented by study visit (i.e., enrollment, Month 3, and Month 6) as a proportion of all enrolled participants (N=50) who responded to the following questions:
 - i. "I feel confident that my health is improved by getting care in a mobile clinic." (Agree, Somewhat agree)
 - ii. "I feel safe getting care in a mobile clinic." (Agree, Somewhat agree)
 - iii. "I am worried about how people will react if they see me getting care at a mobile clinic." (Disagree, Somewhat disagree)
7. Assess acceptability of POC STI testing at community-based site.
- a. Participants completed an acceptability survey following each study visit. Acceptability will be presented by study visit (i.e., enrollment, Month 3, and Month 6) as a proportion of all enrolled participants (N=50) who responded to the following questions:
 - i. "I felt comfortable getting rapid STI testing in the mobile clinic." (Agree, Somewhat agree)
 - ii. "I prefer getting rapid tests for sexually transmitted infections (STI) more than getting traditional STI tests." (Agree, Somewhat agree)

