Design: Pilot of novel care model for low-barrier care and adherence support for uptake and sustained use of biomedical HIV prevention and medications for opioid use disorder for women who inject drugs

Study Population: 50 female-identifying people ≥18 years of age and older who have ever injected drugs and are not known to be HIV-positive

Study Site: Community-based clinic on north Aurora Avenue in Seattle, WA

Primary Study Objectives:

1. Evaluate uptake of PrEP and MOUD
2. Evaluate sustained use of PrEP and MOUD
3. Evaluate treatment completion rate and time to completion after POC STI testing
4. Assess acceptability of pilot community-based care model
5. Assess acceptability of POC STI testing at community-based site.

Approach: We will conduct a pilot study of a community-based novel care model developed with community feedback and a community advisory board (CAB) co-design process during phase I of this project. We will enroll 50 female-identifying people and follow them for 6 months. We will assess uptake of PrEP and buprenorphine; POC STI testing and treatment completion rates; sustained use of PrEP and buprenorphine at months 3 and 6 (n=50). We will conduct surveys, guided by CFIR, to assess and characterize the acceptability and feasibility of venue-based primary and HIV prevention care among women who inject drugs (WWID).

Background and rationale

Women who inject drugs (WWID) experience frequent barriers to receiving primary care, especially sexual health and addiction services, because of perceived stigma, competing needs, and structural inequities within the healthcare system. Barriers to care among WWID are often exacerbated by the additional social chaos of unstable housing and engagement in transactional sex. These structural realities promote exclusion from traditional primary care systems, increase risk of HIV acquisition, and have led to rising rates of syphilis infections and overdose deaths among WWID in recent years. PrEP, buprenorphine, and STI control are key components of the End the HIV Epidemic prevention pillar and proven tools for reducing risk of HIV acquisition and opioid overdose, but uptake and sustained use of these interventions are low among WWID.

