In 2018, our team at the University of Washington established a weekly clinic, the Safe. Healthy. Empowered. (SHE) Clinic, to provide care for WWID and exchange sex. SHE Clinic is co-located and operated in collaboration with Aurora Commons, a not-for-profit drop-in center that provides basic needs and day-shelter for unhoused individuals in Seattle. HIV prevalence is approximately 10% among SHE Clinic patients, with 80% of patients engaging in injection drug use and 69% reporting exchange sex; although internal, unpublished estimates suggest the prevalence of exchange sex may be >90% in the SHE Clinic population. Initially operating only four hours per week, SHE Clinic, under the direction of [name] (co-I), has provided care to over 190 socially and medically marginalized women in Seattle. Nonemergent emergency department visits among SHE Clinic patients significant declined over a six-month period when compared with similar visits among WWID in north Seattle who had never received care at SHE Clinic. Uptake of PrEP (33%) and buprenorphine (49%) among SHE Clinic patients has improved significantly. Significant barriers to care remain for these socially and medically marginalized women. Despite the availability of PrEP and the high prevalence of HIV and HIV-risk factors in this population, sustained use of PrEP is exceedingly low (0-5%) among SHE Clinic patients after six months, as is sustained use of buprenorphine (12%) (**Preliminary Results**).

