We will implement a pilot clinic one evening per week, with the primary goal of measuring a community-based extension of SHE Clinic's impact on uptake and sustained use of HIV pre-exposure prophylaxis (PrEP) and medications for opioid use disorder (MOUD). The clinic will be dispatched with a driver, nurse, physician, and research assistant. The van clinic will be outfitted with space to obtain a confidential history and physical exam and include a space for sample collection. Similarly, the van clinic will be equipped with a WiFi hotspot with a laptop linked to University of Washington's EMR system for clinical documentation, orders, and referrals. In addition to standard of care, (Table 1), we will provide participants with rapid point-of-care HIV and STI testing. All people presenting for a walk-in clinic visit who do not enroll will be offered laboratory-based testing and prescription medications, which are subject to insurance/billing. Women enrolled in the research study will be instructed on self-collection of vaginal swab specimens, which will be tested for *C. trachomatis* and *N. gonorrhoeae* using the 30-minute Binx Health rapid PCR platform. OSOM swabs for trichomonas will be placed into a sterile tube and processed on site with rapid testing kits (Sekisui Diagnostics) along with POC HIV and syphilis testing via finger prick (Chembio Diagnostic Systems). Any samples that cannot be tested using point-of-care methods will be transported to Harborview Medical Center laboratory following clinic sessions. Results will be delivered to participants, either immediately, via cell phone for lab-based tests or when a participant follows up at the mobile clinic or at SHE Clinic. STI treatment will be given per clinical guidelines. Treatment of gonorrhea will consist of intramuscular ceftriaxone 500mg x1. Participants who test positive for chlamydia will be recommended to take doxycycline 100mg PO BID for 7 days; however, azithromycin 1g PO x1 will be offered as an alternative if participants are unable to complete a 7-day course of antibiotics. Similarly, participants who test positive for trichomonas will be recommended to take metronidazole 500mg PO BID for 7 days; however, metronidazole 2g PO x1 will be offered as an alternative if participants are unable to complete 7 days of antibiotics. Early syphilis will be treated with 2.4 million units of benzathine penicillin x1 or oral doxycycline 100mg BID for 14 days, pending benzathine penicillin availability. Late latent syphilis will be treated with 2.4 million units of benzathine penicillin weekly for 3 weeks or oral doxycycline 100mg BID for 28 days, pending benzathine penicillin availability.

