Clinical study visits will occur at enrollment, a follow-up study visit at month-3, and an exit visit at 6-months post-enrollment. For participants who are prescribed buprenorphine, additional brief refill visits will occur at monthly intervals. All assessments will occur during in-person visits in the pilot clinic. Each study visit will consist of a short survey, an eligibility assessment for oral PrEP and MOUD, standard clinical care, and biological sample collections (i.e., DBS sample collection for research only, self-collected vaginal swabs for point-of-care STI testing, and blood samples for blood born infection testing). To test the impact of this pilot clinic model on improving uptake and sustained use of HIV prevention services, we will utilize medical record data and DBS drug (buprenorphine and tenofovir) levels. Prior to enrollment, participants will be asked to provide consent for participation in the study, review of electronic medical record (EMR) data, and review of pharmacy records. Consent will be collected using electronic data capture (REDCap) and participant data will be collected by medical record number (MRN) utilizing an EMR querying technology (Leaf) generated by the University of Washington as well as manual chart review. Participants meeting CDC eligibility criteria for PrEP will be counselled on HIV risk, offered HIV testing, and if negative and interested, oral PrEP will be prescribed per clinical guidelines. Additionally, participants with active self-reported use of opioids will be counselled on options for opioid use disorder treatment, and those interested in MOUD, will be provided with a prescription for buprenorphine-naloxone or buprenorphine, per clinical guidelines. Uptake of PrEP and buprenorphine will be measured by review of pharmacy and EMR records and will be defined by filling a prescription for PrEP or buprenorphine. In collaboration with [name] and the University of California San Francisco (UCSF) Hair Analytical Laboratory (HAL), we will measure sustained use of PrEP and buprenorphine via tenofovir disoproxil fumarate (TDF) and buprenorphine levels in samples of 150 hairs. The UCSF-HAL can simultaneously test for buprenorphine, fentanyl, and tenofovir from the same specimen, and we will measure these drug levels at 3- and 6- months to evaluate adherence to PrEP and buprenorphine. Additionally, dried blood spots (DBS) will be collected and archived to ensure that drug levels are collected during this study in the event there are any complications with hair testing.

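### The protocol claims to test impact and demonstrate benefit, but one uncontrolled cohort summarised by single percentages can only estimate uptake and sustained use

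*Protocol*

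**What the plan says.** All references are to the Protocol.

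**Aim.** Four sections use causal wording:
- Study Design, General Overview: a pilot clinic "with the primary goal of measuring a community-based extension of SHE Clinic's impact on uptake and sustained use" of PrEP and MOUD.
- Data Collection Overview: "To test the impact of this pilot clinic model on improving uptake and sustained use of HIV prevention services".
- Involvement of Human Subjects: the main objective is to "assess the impact of venue-based care on uptake and sustained use of PrEP and buprenorphine".
- Importance of Knowledge to be Gained: "If the study demonstrates benefit of venue-based care, this would provide evidence that this type of intervention should be studied at scale".

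The Primary Study Objectives in the synopsis are worded differently. They say only that uptake and sustained use will be evaluated.

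**Design and analysis.** "This is a prospective observational cohort study, which aims to enroll 50 women who inject drugs in a venue-based clinic". Analysis Plan items 1 to 4 report uptake over all 50 enrolled and sustained use among those prescribed, each as a percentage. No comparator, before period, reference rate or success threshold is named.

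**Sustained use in the pilot.** For PrEP this is a drug level reached "at 3 and/or 6 months post-enrollment among those prescribed PrEP at a preceding study visit". Item 4 uses the same window and denominator for MOUD, with any detectable drug as the criterion.

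**SHE Clinic rates.** The Background gives uptake of 33% for PrEP and 49% for buprenorphine. It adds that "sustained use of PrEP is exceedingly low (0-5%) among SHE Clinic patients after six months, as is sustained use of buprenorphine (12", the last figure being a percentage. It does not say how sustained use was measured at SHE Clinic.

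**The concern.** An aim of testing impact on improving an outcome needs something to compare with. Here there is no second arm, no pre-enrolment period in the analysis and no fixed reference value. Whatever percentages result, the planned analysis cannot say whether they are higher than they would have been without the evening clinic. The document nevertheless foresees the study showing benefit and makes that the condition for further research.

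The lack of a named comparator also invites an informal one. The pilot is presented as an extension of SHE Clinic, and the Background offers SHE Clinic's low six-month rates as the gap to be closed. A reader of the final report would naturally put the new sustained-use percentages next to those rates. The two sets differ in denominator and time window as worded, so part or all of an apparent gain could be produced by the definitions.

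**Working it through.** The protocol gives no alpha, power, reference rate or threshold behind N = 50, so there is no stated calculation to reproduce.

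**1. Aim against analysis.** Measuring, testing or assessing impact requires a contrast. Analysis Plan items 1 to 4 contain none; each is one proportion from one group. The synopsis objectives need no contrast and match those items. The mismatch is therefore between the four sections listed above and the rest of the document.

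**2. Inputs for the informal comparison.**

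| | SHE Clinic (Background) | Pilot (Analysis Plan) |
|---|---|---|
| Uptake, PrEP / buprenorphine | 33% / 49%, per SHE patient as worded | all 50 enrolled |
| Sustained use, PrEP / buprenorphine | 0-5% / 12%, per SHE patient as worded | those prescribed at a preceding visit |
| Time | after six months | month 3 and/or month 6 |
| Measure | not stated | dried-blood-spot level |

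**3. Denominator effect on sustained use.** Assume that the SHE figures are per all patients and that SHE uptake means prescribed. Then sustained use among those prescribed = sustained use among all / uptake. For a pilot performing exactly like SHE Clinic:
- Buprenorphine: 12 / 49 = 24.5%, and 24.5 / 12 = 2.04 times the printed rate.
- PrEP, upper end: 5 / 33 = 15.2%, and 15.2 / 5 = 3.03 times the printed rate.
- PrEP, lower end: 0 / 33 = 0%, no shift.

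If the SHE sustained-use rates are already per starter, the ratio is 1.0 throughout. The plausible range is thus 1.0 to 3.03, and the document does not settle where in it the truth lies.

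**4. How often this would show.** With SHE-like uptake, 50 × 0.33 = 16.5 (about 17) women would be prescribed PrEP and 50 × 0.49 = 24.5 (about 25) buprenorphine. These are exact binomial probabilities with no true effect, under the assumptions of step 3 and PrEP at its upper end:
- Above the printed SHE rate: PrEP, at least 1 of 17, 1 − (1 − 0.1515)^17 = 0.939; buprenorphine, at least 4 of 25, 0.894.
- At least twice the printed rate: PrEP, at least 2 of 17, 0.753; buprenorphine, at least 6 of 25, 0.599.

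Rounding down to 16 and 24 women gives 0.928 and 0.955 for the first line, and 0.722 and 0.555 for the second.

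**5. Precision.** Clopper-Pearson 95% intervals at roughly the expected counts are 3.8% to 43.4% for 3/17 and 9.4% to 45.1% for 6/25. Each interval contains both the printed SHE rate and its re-expressed value.

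**6. Window.** Read as use at either visit, the and/or rule cannot give less than month 6 alone on the same women. If month-3 and month-6 rates were each 24.5% (an assumption), the either-visit rate would lie between 24.5% (same women at both visits) and 24.5 + 24.5 = 49.0% (different women).

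**7. Uptake.** As worded, both sources use everyone in care or enrolled, so the effect in step 3 does not arise. The one difference in case mix that can be sized is HIV status: about 10% of SHE patients have HIV, while known HIV is excluded from the pilot. If the 33% counts all SHE patients, 33 / 0.90 = 36.7%, a ratio of 1.11.

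**8. Measure.** The SHE measure is not given. Any detectable buprenorphine is a lenient criterion. A tenofovir-diphosphate threshold could be stricter than a record-based measure. The direction of any mismatch is therefore unknown.

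**The case against.** A single-arm pilot with descriptive proportions is a legitimate design. The listed primary objectives are descriptive, and the Analysis Plan answers them item by item. The SHE rates appear once, as preliminary results, and are never named as a benchmark. The Background also cites PrEP use of 0-3% among people who inject drugs and buprenorphine retention that may be under 50% at six months. The benefit sentence leads only to further study, an ordinary purpose of a pilot. All of this stands, and it limits the point to aim wording and to how sustained use is tabulated.

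It does not rescue the impact wording. The protocol contains its own Analysis Plan, so the absence of a contrast is fixed here and is not simply a detail deferred to an SAP. Calling the study a pilot does not turn one percentage into evidence of improvement.

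Three stronger readings are tempting and not supported:
- A reader might infer that the protocol plans a biased comparison with SHE Clinic. It plans no such comparison.
- A reader might infer that an ineffective clinic would look two to three times better on all four SHE rates. Uptake denominators match as worded, and for sustained use the factor rests on two assumptions that the document does not confirm.
- A reader might infer that the synopsis contradicts the Analysis Plan's denominator because it promises "sustained use of PrEP and buprenorphine at months 3 and 6 (n=50" with the number in brackets closing the sentence. That number readily reads as the cohort size.

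**Conclusion.** The point holds in a limited form. Three sections state an impact aim and a fourth speaks of demonstrating benefit, while the design and Analysis Plan can deliver only estimates. This conclusion needs no assumption; it follows from the text.

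The caution about SHE Clinic is secondary and conditional. It concerns sustained use only. Its size runs from nil, if the SHE rates are already per starter, to about two-fold for buprenorphine and, for any non-zero SHE rate, three-fold for PrEP, if they are per all patients and SHE uptake means prescribed. The repeated use of the same patient wording for SHE uptake and SHE sustained use favours the all-patient reading but does not prove it. The and/or window could add to the difference, and an unknown difference in measure could move it either way.

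The design itself is not at fault. The aim should be corrected because it governs what the final report may claim, and the correction is easy.

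**What to change.** 1. In the General Overview, Data Collection Overview, Involvement of Human Subjects and Importance of Knowledge to be Gained, restate the aim as estimating uptake and sustained use under the pilot model, in line with the synopsis objectives. Make further study depend on descriptive feasibility and use estimates, not on a demonstration of benefit.
2. In Analysis Plan items 3 and 4, report month 6 separately from month 3, over all enrolled as well as among those prescribed, with confidence intervals.
3. If change is to be discussed, describe it against participants' own baseline use. The baseline questionnaire already covers prior PrEP use and prior and current MOUD use; add pharmacy records where available. Label the comparison as uncontrolled, open to regression to the mean and to incomplete earlier records. Women new to the University of Washington system may have few earlier records, which would undercount prior use and favour apparent improvement.
4. Cite SHE rates only with their denominator, time point and measure stated. Recomputing them on the pilot's drug-level criterion is not an option on the documents, which describe no drug levels from SHE patients.

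Separately, the Data Collection Overview defines uptake by a filled prescription and the Analysis Plan by an accepted one. The two should be reconciled before any rates are compared.

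The cost is protocol wording, slightly more tabulation and a more modest claim. No new visits, samples or participants are needed.
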